9.3.3 Measurable Disease Assessment

The absolute and percent change from baseline for the sum of longest diameters of the baseline target lesions from measurable tumor assessment CRF page will be listed by dose group for phase 1 subjects and summarized and listed by treatment arm for phase 2 subjects at the Best-case post baseline. The summary may be repeated for injected and non-injected lesions separately.

Waterfall plots of the maximum percentage change from baseline in measurable tumor burden (the sum of the longest diameter) will be produced for the phase 2 results. The bars will not be coded for any factor but the treatment combinations will be distinct colors in the separate figures.

Measurable disease assessment, non-measurable disease assessment, assessment of RECIST v1.1 response, assessment of irRECIST response and assessment of irRC response data will be listed by subject. **Exploratory Analyses**

9.4.1 Pharmacodynamic Markers

Analysis of pharmacodynamic result is not in the scope of this analysis plan and will be addressed separately.

9.4.2 Immunogenicity Analyses

Immunogenicity results will be included in data listings only.

10 SAFETY ANALYSES

All safety analyses will be performed on the Safety Population.

10.1 Extent of Exposure

Exposure will be calculated separately for IMO-2125, ipilimumab and pembrolizumab. Total number of doses (injections or infusions) per subject, total volume administered (mL) per subject, total dose administered (mg) for ipilimumab and pembrolizumab only, and the duration of treatment (months) will be summarized by each dose group. Duration of treatment is defined as the (last dose date minus the first dose date plus 1)/30.4375.

Dose modifications will be reported separately for IMO-2125, ipilimumab and pembrolizumab.

Dose modifications for IMO-2125 will be described by summarizing:

- the number of subjects who had an injection delayed. The “injection delayed” determination will be based on the answer to the question of “Was Intratumoral Injection delayed?” on the “Study Drug Administration (IMO-2125)” CRF pages. The summary will be presented by dose group and overall as well as by cycle (phase 1) and by treatment arm (phase 2), with each injection given representing a new cycle.
- the number of subjects who had dose decreased. The “dose decreased” determination will be based on the answer to the question of “Was planned dose decreased? on the “Study Drug Administration (IMO-2125)” CRF pages. The summary will be presented by dose group and overall as well as by cycle (phase 1) and by treatment arm (phase 2), with each injection given representing a new cycle.

Dose modifications for ipilimumab and pembrolizumab will be described by summarizing:

- the number of subjects who had infusion rate decreased. The “infusion rate decreased” determination will be based on the answer to the question of “Was Infusion Rate decreased?” on the ipilimumab and pembrolizumab infusion CRF pages. The summary will be presented by dose group and overall as well as by cycle, with each infusion given representing a new cycle.
- the number of subjects who had infusion discontinued. The “infusion discontinued” determination will be based on the answer to the question of “Was Infusion Discontinued? on the ipilimumab and pembrolizumab infusion CRF pages. The summary will be presented by dose group and overall as well as by cycle, with each injection given representing a new cycle.
- the number of subjects who had infusion interrupted. The “infusion interrupted?” determination will be based on the answer to the question of “Was infusion interrupted? on the ipilimumab and pembrolizumab infusion pages. The summary will be presented by dose group and overall as well as by cycle (phase 1) and by treatment arm (phase 2), with each infusion given representing a new cycle.

Data listings for study drug administered will be provided.

10.2 Adverse Events

Adverse event summaries will be restricted to Treatment Emergent Adverse Events (TEAE), which are defined as those AEs that started on or after the date of first dose of study treatment and those existing AEs that worsened during the study. If it cannot be determined whether the AE is treatment emergent due to a partial onset date, then it will be counted as treatment emergent. Verbatim terms on electric case report forms will be mapped to preferred terms and system organ classes using the Medical Dictionary for Regulatory Activities (MedDRA) (version 16.1).

Summaries displayed by system organ class and preferred terms will be ordered by descending order of incidence of system organ class and preferred term within each system organ class, with TEAEs of the same incidence displayed alphabetically. Summaries displayed by preferred term will be ordered by descending order of incidence, with TEAEs of the same incidence displayed alphabetically.

Summaries of the following types will be presented:

- Overall summary of TEAEs which contain an overview of number of subjects with at least one TEAE, at least one IMO-2125-related TEAE, at least one ipilimumab-related TEAE, at least one pembrolizumab-related TEAE, at least one serious TEAE, at least one grade 3 or higher TEAE, at least one TEAE leading to discontinuation, at least one TEAE of action taken with IMO-2125 as drug withdrawn, at least one TEAE of action taken with ipilimumab as drug withdrawn, at least one TEAE of action taken with pembrolizumab as drug withdrawn, at least one immune-related TEAE, and at least one TEAE with fatal outcome. The maximum severity by the CTCAE will also be included.
- Subject incidence of TEAEs by MedDRA SOC and preferred term.
- Subject incidence of TEAEs by preferred term.
- Subject incidence of TEAEs by preferred term, and highest Common Terminology Criteria for Adverse Events (CTCAE) toxicity grade. At each level of subject summarization, a subject is classified according to the highest CTCAE toxicity grade if the subject reported more than one event.
- Subject incidence of IMO-2125-related TEAEs by preferred term. Only those AEs reported as “Related”, “Possibly”, or “Probably”, or which have a missing relationship to IMO-2125 will be included in this summary.
- Subject incidence of ipilimumab-related TEAEs by preferred term. Only those AEs reported as “Related”, “Possibly”, or “Probably”, or which have a missing relationship to ipilimumab will be included in this summary.

- Subject incidence of pembrolizumab-related TEAEs by preferred term. Only those AEs reported as “Related”, “Possibly”, or “Probably”, or which have a missing relationship to pembrolizumab will be included in this summary.
- Subject incidence of serious TEAEs by preferred term.
- Subject incidence of IMO-2125-related serious TEAEs by preferred term. Only those AEs marked as “Related”, “Possibly”, or “Probably”, or which have a missing relationship to IMO-2125 will be included in this summary.
- Subject incidence of ipilimumab -related serious TEAEs by preferred term. Only those AEs reported as “Related”, “Possibly”, or “Probably”, or which have a missing relationship to ipilimumab are considered for this summary.
- Subject incidence of study pembrolizumab serious by preferred term. Only those AEs reported as “Related”, “Possibly”, or “Probably”, or which have a missing relationship to pembrolizumab are considered for this summary.
- Subject incidence of TEAEs that have CTCAE grade 3 or higher by preferred term.
- Subject incidence of TEAEs leading to study discontinuation by preferred term.
- Subject incidence of TEAEs of action taken with IMO-2125 as drug withdrawn by preferred term.
- Subject incidence of TEAEs of action taken with ipilimumab as drug withdrawn by preferred term.
- Subject incidence of TEAEs of action taken with pembrolizumab as drug withdrawn by preferred term.
- Subject incidence of immune-related TEAEs by preferred term.
- Subject incidence of TEAEs with fatal outcome by preferred term.
- Subjects with non-serious TEAEs by SOC and preferred term.

irAEs will be determined from a list of pertinent MedDRA codes provided by the study sponsor.

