ICH	International Council for Harmonisation
IMO	Immune Modulatory Oligonucleotide
irAE	Immune-related adverse event
irRC	Immune-related response criteria
irRECIST	Immune-related reponse evaluation criteria solid tumors
ISR	Injection site reaction
LFT	Liver function test
MLE	Maximum Least-square Estimation
MTD	Maximum tolerated dose
NCI	National Cancer Institute
ORR	Objective response rate
OS	Overall survival
PD	Progressive disease
PFS	Progression-free survival
PI	Principal Investigator
PK	Pharmacokinetic
PR	Partial response
Pr	Probability
PRO	Patient reported outcome
PT	Prothrombin time
RBC	Red blood cell
RP2D	Recommended Phase 2 dose

SAE	Serious adverse event
SD	Stable disease
ULN	Upper limit of normal
WBC	White blood cell

DEFINITIONS

Adverse Event	An adverse event (AE) is any reaction, side effect, or other untoward event, regardless of relationship to study drug, which occurs anytime during the study.
DLT Evaluable Population	All subjects in the Safety Population who continue participation in the study for the entire DLT evaluation period, or who discontinue prematurely due to a DLT.
DLT Evaluation Period	The DLT evaluation period will be Cycle 1 (Weeks 1 through 4).
Safety Population	All subjects who received at least one dose of IMO-2125.
Serious AE	An AE occurring at any dose that: results in death; is a life-threatening experience; requires hospitalization or prolongation of an existing hospitalization; results in a persistent or significant disability/incapacity; or is a congenital anomaly/birth defect in the offspring of a subject who received study drug; or important medical event that, although not immediately life-threatening, requires intervention in order to prevent one of the listed serious outcomes listed.
Study Drug	IMO-2125 in combination with ipilimumab or pembrolizumab
Treatment-emergent AE	AEs with an onset date on or after the date of the initial dose of study drug, or an AE that worsens after the date of the initial dose of study drug.

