3. STUDY DESIGN AND PLAN

3.1 Overview

This is a two arm open-label Phase 1/2 study to assess the safety, tolerability, PK, immunogenicity, and efficacy of IMO-2125 when administered in combination with ipilimumab or in combination with pembrolizumab. Subjects with metastatic melanoma who have experienced symptomatic or confirmed radiographic progression to their most recent treatment regimen (anti-PD-[L]1 alone or in combination) will be eligible. Prior BRAF or MEK inhibitor treatment is not required. The study will be conducted in two parts: a dose-escalation portion (Phase 1) to evaluate safety and tolerability of multiple dose levels and a Phase 2 portion to assess preliminary efficacy.

3.1.1 Phase 1

The Phase 1 portion of the study is will explore escalating dose levels of IMO-2125 (from 4 to 32 mg with de-escalation to 2 mg allowed for each IMO-2125 combination). For each cohort, IMO-2125 will be administered as a once-weekly intratumorally injection for 3 consecutive weeks in Cycle 1, followed by intratumorally injections on Weeks 5, 8, 11, 17, 23, and 29 (Day 1 of Cycles 2 through 7). Both ipilimumab and pembrolizumab will be administered as per the USPI every 3 weeks beginning Day 1 of Week 2. Continued dosing of pembrolizumab following the study treatment period is permitted at the discretion of the Investigator for subjects in the IMO-2125 + pembrolizumab treatment arm. The dosing schedule is summarized in Table 1.

Table 1: Schedule of Dosing for Phase 1 and Phase 2

	Cycle															
	1				2			3			4			5	6	7
Study week	1	2	3	4	5	6	7	8	9	10	11	12	13	17	23	29
IMO-2125 + ipilimumab																
IMO-2125	X	X	X	-	X	-	-	X	-	-	X	-	-	X	X	X
Ipilimumab	-	X	-	-	X	-	-	X	-	-	X	-	-	-	-	-
IMO-2125 + pembrolizumab																
IMO-2125	X	X	X	-	X	-	-	X	-	-	X	-	-	X	X	X
Pembrolizumab	-	X	-	-	X	-	-	X	-	-	X	X ¹				

Note: On weeks when the combinations are administered, administration of ipilimumab or pembrolizumab will be first, followed by IMO-2125. IMO-2125 administration must occur within a ±2 day window of the scheduled dosing day.

¹ For subjects in the IMO-2125 + pembrolizumab treatment arm, continued pembrolizumab dosing per the approved product label is permitted at the discretion of the Investigator

Subjects assigned to 11 weeks of IMO-2125 under previous versions of the protocol who have not yet reached the end of the Treatment Period may receive the Week 17, 23, and 29 injections at the discretion of the treating Investigator.

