3.2.2 Study Duration and Study Completion

The study ends approximately 1 year after the last subject in Phase 2 has commenced study treatment. Subjects who complete or discontinue study treatment prior to progression will be followed for clinical and radiological evidence of progression and immunogenicity assessment at least every 3 months until documentation of RECIST v1.1 progressive disease (PD), start of a subsequent anti-cancer treatment regimen, withdrawal of consent, death, or Sponsor notification that follow-up is no longer required, whichever comes first. Best response to first subsequent therapy, AEs which are Grade ≥ 3 , and concomitant medications used to treat these AEs, will also be captured during the follow-up phase of the study (Table 4 and Table 5).

After documentation of PD or use of a subsequent anti-cancer treatment regimen, all subjects will be contacted by telephone every 3 months for a survival follow-up until the site is notified by the Sponsor that survival follow-up is no longer required. A subject has completed the study at the earliest of death or study end.

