³ Includes ongoing follow-up every 3 months until documented disease progression, next melanoma treatment, withdrawal of consent, death, or Sponsor notification that follow-up is no longer required.

⁴ All assessments and IMO-2125 dosing will occur within a \pm 2-day window. Ipilimumab and pembrolizumab will be dosed per their respective labels.

⁵ All Screening tests and assessments must be performed within 21 days of the start of Week 1 of Cycle 1, unless otherwise noted. All patients who sign an informed consent and are screened and qualify for the study will be considered enrolled.

⁶ Including melanoma history and prior melanoma treatment history.

⁷ Grade ≤ 2 AEs do not need to be reported.

⁸ Only concomitant medications for the treatment of Grade ≥ 3 AEs will be captured.

⁹ CBC with differential should be done 24 to 48 hours after the IMO-2125 injection, to coincide with the post-injection biopsy. Chemistry profile and coagulation tests do not have to be conducted if Screening tests were conducted within 7 days of the Cycle 1 Week 1 Visit.

¹⁰ PT, aPTT, INR.

¹¹ Blood pressure, heart rate, respiratory rate, and temperature.

¹² Week 2 ECG pre-dose and at 2 hours post-IMO-2125 administration. Week 11 ECG at 2 hours post-IMO-2125 administration.

¹³ Including assessment of melanoma lesions.

¹⁴ Biopsy of the tumor to be injected with IMO-2125 and biopsy of a tumor that will not be injected. See Section 13.2 of the protocol and the Laboratory Manual for details on the collection of biopsies and analyses of biomarkers.

¹⁵ Biopsy of the injected tumor should occur within 24 to 48 hours after injection (no more than 48 hours). Collection of blood for biomarkers should occur on Day 1 pre-IMO-2125 administration, 4 hours after IMO-2125

administration, and 24 to 48 hours after injection (coinciding with the 24-hour PK sample). At Week 2, collect before ipilimumab or pembrolizumab dosing.

¹⁶ Optional biopsy.

¹⁷ At Weeks 5 and 8, collect pre-ipilimumab or pre-pembrolizumab dosing and post-IMO-2125 dosing. At Week 29/EOT collect pre-pembrolizumab dosing (for subjects in that arm who have pembrolizumab continued) and post-IMO-2125 dosing. If no ipilimumab or pembrolizumab is given at the specified visit(s) collect the samples pre- and post-IMO-2125 dosing. If no IMO-2125 if given, then collect pre- and post- ipilimumab or pembrolizumab.

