Coagulation ¹⁰	X	X ₉			X	X	X			X		X		X	X
Chemistry profile	X	X ₉	X	X	X	X	X			X		X		X	X
Thyroid functions	X		X		X	X	X			X		X		X	X
CH50/C3/C4	X				X	X	X			X		X		X	X
Urinalysis	X					X				X					X
Vital signs ¹¹	X	X	X	X	X	X	X			X		X		X	X
ECG	X		X ₁₂				X ¹²								X
Directed physical ¹³	X	X			X	X	X			X		X		X	X
Pregnancy test	X														X
Tumor biopsies/biomarkers ¹⁴	X	X ₁₅	X			X		X				X			
Blood biomarkers		X ₁₆	X ₁₆			X ¹⁶									
Radiology	X					X ₁₇			X ₁₇				X ¹⁷		X ¹⁸
Response ¹⁹						X ₁₇			X ₁₇				X ¹⁷		X ¹⁸
PRO ²⁰		X				X			X				X		X ¹⁸
IMO-2125 dosing		X	X	X	X	X	X		X		X		X		
Ipilimumab dosing		X		X	X	X									
Pembrolizumab dosing			X		X	X	X		X	X	X	X	X	X ²¹	X ²¹
PK testing ²²		X	X	X	X	X	X		X ₂₃		X ₂₃		X ²³	X ²³	
Immunogenicity ²⁴		X			X		X		X		X		X	X	X ²⁵

Abbreviations: AE=adverse event; aPTT=activated partial thromboplastin time; C3=complement component 3; C4=complement component 4; CBC=complete blood count; CH50=total hemolytic complement activity 50; CR=complete response; CT=computed tomography; Demogr=Demographic; diff=differential; ECG=electrocardiogram; ECOG=Eastern Cooperative Oncology Group; EOT= End of Treatment; hx=history; INR=international normalized ratio; irRC=immune-related response criteria; med=medical; PK=pharmacokinetic; PR=partial response; PRO = patient reported outcomes; PT=prothrombin time

¹ Please note, the number of weeks per cycle varies. Cycle 1 is 4 weeks in length to account for an IMO-2125 priming dose. Cycles 2, 3, and 4 are 3 weeks in length, and Cycles 5, 6, and 7 are included as maintenance dosing and are 6 weeks in length.

² The Safety Follow-up Visit should be 21 days following the last dose of IMO-2125 (\pm 5 days).

³ Includes ongoing follow-up every 3 months until documented disease progression, next melanoma treatment, withdrawal of consent, death, or Sponsor notification that follow-up is no longer required.

⁴ All assessments and IMO-2125 dosing will occur within a \pm 2-day window. Ipilimumab and pembrolizumab will be dosed per their respective labels.

⁵ All Screening tests and assessments must be performed within 21 days of the start of Week 1 of Cycle 1, unless otherwise noted. All patients who sign an informed consent and are screened and qualify for the study will be considered enrolled.

⁶ Including melanoma history and prior melanoma treatment history.

⁷ Grade \leq 2 AEs do not need to be reported.

⁸ Only concomitant medications for the treatment of Grade \geq 3 AEs will be captured.

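### TEAEs have no end date while follow-up requires only Grade ≥3 reporting, so the all-grade, maximum-grade, related and immune-related tables pool two levels of ascertainment

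*SAP*

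**What the plan says.** **Analysis definition.** SAP Section 10.2 limits the adverse-event summaries to treatment-emergent events: "those AEs that started on or after the date of first dose of study treatment and those existing AEs that worsened during the study". The Definitions list says the same, "AEs with an onset date on or after the date of the initial dose of study drug" or worsening after that date, and describes an adverse event as one "which occurs anytime during the study". Neither place sets a last day, whether counted from the last dose, a visit or the start of new therapy.

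**Collection.** Section 3.2.2 says that AEs of Grade 3 or higher "and concomitant medications used to treat these AEs, will also be captured during the follow-up phase of the study". Footnote 7 to the Phase 1 schedule (Table 4) states: "Grade ≤ 2 AEs do not need to be reported". The Phase 2 schedule (Table 5) has the same footnote. In both tables the marker is on the last entry of the adverse-events row, read here as the ongoing follow-up column. The Safety Follow-up Visit is 21 days (±5) after the last IMO-2125 dose.

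**Tables.** Section 10.2 and Appendix E list subject incidence by preferred term, by preferred term and highest grade, by relationship to each drug, and for immune-related events. All use every treatment-emergent event. No on-treatment or follow-up split is planned.

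**The concern.** A table that reports all grades is interpretable when all grades were sought for the whole period it covers. Here a Grade 1 or 2 event that starts in ongoing follow-up may never be recorded, while a Grade 3 event in the same week is recorded and enters the same row.

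The switch point also varies between subjects. It falls at about Week 32 after a Week 29 dose and at about Week 14 after a Week 11 dose. The second case can apply to the group described in the note to Table 1 as "Subjects assigned to 11 weeks of IMO-2125 under previous versions of the protocol", although those still on treatment may receive the later injections. It is earlier again for early discontinuers. How long Grade ≥3-only collection then lasts depends on when the subject progresses or starts new therapy. In the pembrolizumab arm, subjects may still be receiving pembrolizumab during that time.

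At stake is the reading of the descriptive safety tables: how often a term occurs at any grade, and how severe it tends to be when it occurs. Safety is part of the Phase 1 primary objective and a Phase 2 secondary objective.

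**Working it through.** The SAP states no figure on this point, so there is nothing to reproduce. The check is a counting argument, followed by illustrations with assumed inputs.

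**1. Direction.** For one preferred term, let

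- a = subjects with the event in the full-collection period, and s = those of them at Grade ≥3;
- l = further subjects whose only events are Grade 1–2 in follow-up (not required to be reported);
- h = further subjects with a Grade ≥3 event in follow-up (reported).

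The Grade ≥3 share among subjects with the term is then

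- as planned: (s+h)/(a+h);
- with complete collection: (s+h)/(a+l+h);
- in the full-collection period alone: s/a.

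Because l and h are not negative and s ≤ a, the planned share is never below either of the others. All-grade incidence as planned, (a+h)/N, is never above (a+l+h)/N. Grade ≥3 incidence, (s+h)/N, is the same with planned and complete collection. If sites choose to report some low-grade events, l shrinks but the direction stays.

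**2. Illustration by preferred term.** N = 60 is the Phase 2 ipilimumab ceiling in Section 3.1.2. The event counts are assumptions.

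| a, s, l, h | Full period only | As planned | Complete | All-grade incidence, planned vs complete |
|---|---|---|---|---|
| 12, 3, 0, 0 | 3/12 = 25% | 3/12 = 25% | 3/12 = 25% | 20.0% vs 20.0% |
| 12, 3, 3, 1 | 3/12 = 25% | 4/13 = 31% | 4/16 = 25% | 21.7% vs 26.7% |
| 12, 3, 6, 2 | 3/12 = 25% | 5/14 = 36% | 5/20 = 25% | 23.3% vs 33.3% |
| 12, 3, 2, 2 | 3/12 = 25% | 5/14 = 36% | 5/16 = 31% | 23.3% vs 26.7% |
| 0, 0, 3, 1 (late-onset term) | none | 1/1 = 100% | 1/4 = 25% | 1.7% vs 6.7% |

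In the second row, Grade ≥3 incidence is 4/60 = 6.7% with planned and with complete collection.

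**3. Sensitivity to the low-grade rate.** Now take subjects with any event. Assume constant rates: Grade ≥3 at 0.02 per month, low-grade at λ per month, 12 months of follow-up, and full collection for 7.1 months (31 weeks to Day 1 of Week 32: 31 × 7 / 30.4375 = 7.1).

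- As planned: (1 − e^(−0.02×12)) / (1 − e^(−7.1λ − 0.02×12))
- Complete: (1 − e^(−0.02×12)) / (1 − e^(−12(λ+0.02)))

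The numerator is 0.2134.

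| λ per month | As planned | Complete |
|---|---|---|
| 0.10 | 34.8% | 28.0% |
| 0.3 | 23.5% | 21.8% |
| 0.5 | 21.8% | 21.4% |

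The gap closes as low-grade events become common during treatment. It stays wide where few subjects have had the event before the switch, which is the late-onset case in the last row of step 2.

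**The case against.** The best defence is that the distorted quantity is not itself a planned output. Section 10.2 plans subject incidence in the Safety Population, and a reader must divide one count by another to get a Grade ≥3 share. That is true, and it narrows the point, but a table by preferred term and highest grade invites that reading, and all-grade incidence is a direct output.

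Second, an open-ended window is defensible because it keeps late immune-related and fatal events in the main tables. This stands against simply ending the TEAE period 21 days after the last IMO-2125 dose, which would move events during continued pembrolizumab out of those tables. It does not justify leaving the change in collection unmarked.

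Third, the size may be small. The rate of 0.10 per month implies that only 1 − e^(−0.12×7.1) = 57% of subjects would have any event by about Week 32. That may be low for repeated injections plus a checkpoint inhibitor, and nothing in the SAP supports it. The model also keeps the low-grade rate unchanged after treatment ends.

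A reader might infer more than the SAP supports:

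- **That Grade ≥3 incidence is inflated.** It is not, since those events are collected in both periods.
- **That dose or stopping decisions are affected.** Escalation, the MTD and the Phase 2 stopping table use first-cycle DLTs, and the immune-related trigger in Section 3.1.6 counts Grade ≥3 events.
- **That serious events of Grade 2 or lower go unreported.** A schedule footnote does not settle this; serious-event reporting is ordinarily set in the protocol.
- **That a fixed fraction of each subject's first year has full collection.** Ongoing follow-up ends at progression or new therapy, so a 52-week denominator does not fit every subject.
- **That the earlier 11-week assignment biases results by a known amount.** The SAP does not say how many subjects stayed on it.

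**Conclusion.** The point holds in a limited form. As written, the plan pools full-grade and Grade ≥3-only collection in the same all-grade, maximum-grade, related and immune-related tables. The direction is certain: all-grade incidence is unchanged or understated, and the Grade ≥3 share among subjects with a term is unchanged or overstated. The size cannot be derived from the SAP. Under the assumed inputs it runs from nothing to 11 percentage points (36% against 25%) for a term already seen on treatment. For a term seen only in follow-up it can be extreme (100% against 25%, on one reported case). For any-event summaries it is under 2 points once the low-grade rate reaches 0.3 per month.

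The conclusion assumes that full-grade collection ends at the Safety Follow-up Visit. The SAP does not say so in words; it is read from the footnote's position in the schedule tables and needs confirming against the protocol. If collection narrows at another visit, the cut-off moves but the argument does not change.

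**What to change.** In Section 10.2, the Definitions and Appendix E:

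1. Keep the Grade ≥3, serious, fatal-outcome and drug-withdrawn tables over the whole study.
2. Restrict the all-grade, maximum-grade, related and immune-related tables to events with onset up to the end of full-grade collection, taken as the Safety Follow-up Visit once confirmed against the protocol.
3. Add a table of later Grade ≥3 events with the corresponding follow-up time, identifying those that occurred during continued pembrolizumab.
4. Footnote the collection limit on every table that extends beyond that point.

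The cost is SAP wording and one or two extra tables from data already collected. The trade-off is that, for the all-grade summaries, late Grade ≥3 events appear in a separate display; they remain in the whole-study Grade ≥3 table.
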